 - o Increased Stromal Cell Derived Factor 1 (SDF-1) mRNA in endothelial progenitor cells which are low in chronic wounds and ischaemia (8)
- Fibroblasts: increase Proliferating Cell Nuclear Antigen (PCNA), stimulate proliferation and regulate myofibroblast differentiation (13, 25)
- Decrease inflammation by decreasing leucocytes and Tumour Necrosis Factor alpha (TNF- α) (13).

On samples taken and analysed of human wounds treated with ESWT there was found to be higher levels of von Willebrand Factor (vWF), VEGF, endothelium Nitric Oxide Synthase (eNOS), stimulating angiogenesis; higher levels of PCNA, Endothelial Growth Factor (EGF) for increasing cellular proliferation and lower Terminal deoxynucleotidyl transferase dUTP nick end labelling (TUNEL) assay signifying a lower rate of apoptosis (10, 13). Clinically wounds treated with ESWT have a higher epithelisation rate, smaller wound size, better blood flow and better long term healing for up to one year compared to control groups (12, 14-18, 26).

Less is understood about the bactericidal mechanism of ESWT. Studies into the effect of low energy shockwaves on *staphlococcus aureus* have shown in vitro ESWT is more effective at eradicating metabolically active bacteria, has a dose dependent response and in combination with antibiotics such as fosfomycin, cefuroxime and rifampicin is highly effective in eliminating bacteria (27, 28). The hypothesised mechanism is derangement of organelles and DNA through free radical formation.

Aims

The study aims to assess the feasibility of delivering ESWT to patients with diabetic foot wounds and ulcers, investigate the clinical effect of ESWT on wound healing, explore the potential mechanism of action and assess whether it offers any patient reported benefits.

Primary Aim:

- To assess the feasibility of delivering extracorporeal shockwave therapy to patients with a diabetic foot wound.

Secondary Aim:

- Assess the clinical outcomes associated with ESWT on diabetic foot wounds
- Define the mechanism of action of ESWT on wound healing
- Find the effect of ESWT on patient's quality of life
- Understand patient ideas, beliefs and expectations of ESWT

Design

A single centre mixed methods cohort study.

Setting

The study will be conducted in the Academic Vascular Surgical Unit Hull York Medical School at Hull Royal Infirmary. Patients will be recruited from Diabetic Foot Clinic and ward 7 and 70.

Sample Size

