The sample size will be 40. This is appropriate for a feasibility study and is similar to studies of diabetic foot wounds treatment with standard therapy. Interviews will be conducted until data saturation.

Target Population and Recruitment**Inclusion Criteria**

- Diagnosis of diabetes mellitus
- Open wound of the foot
- ABPI >0.8
- Age greater than 18 years old
- Able and willing to give written informed consent
- Be able to adhere to protocol and attend all follow up appointments

Exclusion Criteria

- Pregnancy or breast-feeding
- Current malignancy
- Allergy to materials used in the treatment
- Palliative
- Unable or unwilling to give consent
- Anticoagulation

Screening and Consent

Patient Identification

Potential participants will be identified from the diabetic foot clinic, vascular ward, endocrinology ward and the vascular theatre lists. We will liaise with the appropriate clinical team before approaching potential patients to ensure suitability. If suitable we will introduce the study to the patient, explain what is involved and provide the patient information sheet (Patient Information Sheet Version 3.1 April 2019).

Patient Consent

Informed consent will be taken from participants who express an interest in taking part. We will ensure the participant understands the purpose of the study, what is involved, the possible risks and reinforce the participant is not obliged to take part. The discussion will be documented on the consent form (Consent Form Version 2.1 April 2019).

Following project review (July 2019), all participants will be offered the opportunity to take part in qualitative interviews. New participants will be asked for consent at the start of the study, whereas existing participants will be approached either at a follow up appointment or by telephone. For the latter, we will explain what is involved and provide them with a copy of the Qualitative Study Patient Information Sheet (Version 1.0 April 2019).

Evaluation

Baseline data will be collected from all consenting participants includes:

- Informed consent
- Participants name, date of birth, NHS number, HEY number, address, contact number and name and address of their registered GP
- Past medical and surgical history
- Co-morbidities
- Assessment of concurrent medications
- Smoking history
- Allergy status
- Pregnancy test, if applicable
- BMI
- Baseline pain score
- Baseline quality of life
- Surface area of the wound

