- Physical examination, including level of neuropathy and vital observations
- Ankle Brachial Pressure Index

Restrictions

Dietary

There are no dietary restrictions.

Smoking

Smoking will not be permitted in the Study Centre or in hospital groups except in designated smoking areas.

Concurrent medications

Concurrent medications and new medications commenced during the trial will be recorded. Patients taking anti-coagulation medication will be excluded.

Study Protocols

Study Treatments

Extracorporeal shockwave therapy will be applied using the PeizoWave 2 shockwave system within the device's licensing. The shockwave therapy will be given at 120 pulses/cm², penetration 5mm at a dose of 0.1mJ/mm² at 5 pulses/second (17). Participants will receive 3 sessions of shockwave therapy in a 7-day period alongside standard wound care.

Environmental Conditions

Patients will be assessed and treated at the Diabetic Foot Clinic, Brocklehurst Centre, ward 7/70, Hull Royal Infirmary and/or Academic Vascular Unit, Hull Royal Infirmary.

Outcome measures

Primary outcome

Feasibility of delivering extracorporeal shockwave therapy to patients with a diabetic foot wound, assessed by:

- Recruitment rate
- Adherence in treatment
- Follow up rate
- Reason for exclusions
- Reason for drop outs

Secondary outcomes:

Clinical outcomes:

- Change in wound volume – assessed on 3D imaging

- Incidence of infection – from positive wound swabs and clinical evidence of infection
- Incidence of amputation

Mechanism of action outcomes:

- Assess local tissue perfusion flow changes – using Doppler Flowmetry
- Assess local tissue integrity – using Vapometer
- Assess local bacterial growth - from bacterial analysis from wound swabs

Patient Outcomes

- Changes in quality of life – assessed on the EQ-D5-3L and SF-12
- Changes in pain score – assessed on Visual Analogue Scale and Brief Pain Inventory
- Acceptability and tolerability – assessed on Visual Analogue Scale

Qualitative Outcomes:

- Patient's beliefs around shockwave therapy
- Patient's reported willingness to try new treatments and motivation for that behaviour
- Patient's experience of undergoing shockwave therapy
- Patient's perceived effect of shockwave therapy on their life

As assessed during qualitative in depth interviews

Assessments

1. Quantitative Measures:

Baseline

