After consent participant's baseline data, wound measurements, local perfusion, tissue integrity and wound swabs will be taken and quality of life and pain questionnaires will be completed at baseline before the first treatment.

Follow-up

The participant will receive 3 treatments in the first 7 days after surgery. After the third wound measurements, Vapometry, Laser Doppler Flowmetry and wound swabs will be taken and quality of life, pain and tolerability questionnaires will be completed. Wound imaging, quality of life and pain scores will then be repeated at weeks 4, 8 and 12. Infection and amputation rate will be recorded at each contact with the research team.

2. Qualitative Interviews:

We will conduct semi-structured interviews after the last treatment of ESWT. The interviews will be undertaken in a way acceptable to the patient. They may take place in person or over the phone or be located in the hospital and occur at a time convenient for the patient. The interviews will last 30-40minutes.

If the patient gives their permission interviews will be recorded on a digital device that is password protected.

The interviews will explore the participant's experience of undergoing ESWT. We will draw on previous research investigating patient's experience of different therapies to treat wounds to create a focused topic guide but also allows for flexibility into areas not previously considered by the researcher or identified in the literature (29-32). The topic guide will include patient experience in attending for treatment, experience of receiving ESWT, experience after ESWT and any effect it has had on their life.

The researcher will be supervised by experts in qualitative research based at the University of York and the Academic Vascular Surgery Unit, Hull University Teaching Hospitals.

3. Clinician Surveys:

We will explore clinician stakeholder's beliefs of extracorporeal shockwave therapy through questionnaires. We will approach vascular surgeons and trainees, endocrinologists, infectious diseases specialists and podiatrists. Our aim is to explore their opinion of offering ESWT to acute wounds, knowledge of the evidence base, reservations they may have, willingness to refer for ESWT and potential to deliver the therapy in their clinics.

Concurrent Medications

No restrictions of medications.

Assessment of Concomitant Medications

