Concomitant medications at the start of the trial will be recorded. Any subsequent medication prescribed during the trial period will also be recorded.

Method of Analysis:

Quantitative Data

Recruitment rate, reasons for exclusion and non-consent, as well as follow-up rates and reasons for drop-out (where known) will be presented descriptively. Compliance with treatment will be presented descriptively.

Continuous patient reported and clinical outcomes will be presented as means and standard deviations and categorical outcomes as counts and percentages as at all available follow-up points. Outcomes over time will be summarised graphically where appropriate. Any change in outcomes will be presented with 95% confidence intervals.

Data will be analysed using the SPSS software package.

Qualitative Analysis

We will use thematic analysis approach to data analysis using the phases described as Braun and Clarke, 2006 for analysis of the interviews(33). We will complete the following steps (33):

1. Familiarisation: the interviews will be transcribed and re-read to ensure familiarity with the generated data
2. Code generation: from reading through the interviews potential codes will be assigned to the data
3. Identifying theme: after codes have been assigned they will be reviewed and grouped into themes
4. Reviewing themes: to ensure the themes represent the data we will compare the theme to the codes and the data from which they were derived, in doing this we will create a thematic map of analysis
5. Define theme: we will explore each theme separately, looking at the codes and extracts, to assign names to the themes. The themes will be compared for fit with the rest of the data
6. Produce a report: thematic analysis, along with example extracts, will be reported to answer our research question and be discussed in the context of existing literature

The data will be transcribed using NVIVO and reviewed by two researchers ([name]) to ensure internal validity. The results discussed between three researchers ([name]) to ensure appropriate interpretation. The results will be also be reviewed by the University of York Masters supervisors to reduce any researcher associated bias.

Adverse events

Any Serious Adverse Events will be reported to the Sponsor and National Research Ethics Service recognised Research Ethics Committee. All side effects reported will be recorded throughout the study.

The Device

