- Undergo angioplasty, bypass grafting or further surgery
- Experience an adverse event or reaction
- Die

Overall timescale for the study

Recruitment will begin when Ethics and Trust Research and Development approval has been gained. The patients will be involved in the trial for 12 weeks.

Follow up assessments

Where possible all follow up will coincide with standard dressing and clinic follow ups to minimise the additional visits for participants. The follow up weeks are 4, 8, 12 after randomisation.

Data management

Data will be handled in line with the Data Protection Act 1998. The trial data will be registered with the local Data Protection officer.

For participants entering the study after the second amendment data will be handled in line with the GDPR 2018 guidelines. Patients will also be given information relating to this in the patient information sheets.

The data will be collected entered onto a excel spreadsheet created by the research team. The data will be kept on password protected NHS trust computers with firewalls and antivirus software on files with limited access to the trial investigators.

The storage of data will be in line with the IT department standards. Data will remain on the servers and be backed up on secure HEY IT systems. The data will be accessible to investigators and those seeking permission for monitoring and auditing.

Paper records will be stored and locked in the Academic Vascular Unit when not in use.

Study Report

The final pilot study report will outline the background, methods, results, discussion and conclusion of the trial in line with the CONSORT guidelines. The data from the participants will be anonymous. It will be submitted for publication in a peer-reviewed journal.

Administration

Participant Reimbursement

There is no provision for participant reimbursement. The trial follow up will coincide with routine follow up appointments.

Finance

Sponsors will not influence the trial or its publication.

References

1. Excellence NIoC. Clinical Care Summary: Diabetes - type 2. 2016.
3. Boulton AJ. The diabetic foot: grand overview, epidemiology and pathogenesis. Diabetes Metab Res Rev. 2008;24 Suppl 1:S3-6.
4. Excellence NIoC. Clinical Care Summaries: Diabetic Foot Problems: Prevention and Management. 2016.
5. Facts and Stats [press release]. October 2016.

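### Participants who need further surgery or revascularisation leave the study and no missing-data method is stated, so change over time can look too favourable; a mixed model corrects this only in part

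*Combined protocol and SAP*

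**What the plan says.** The study is described under Design as "A single centre mixed methods cohort study", so there is no control group. The primary outcome is "Feasibility of delivering extracorporeal shockwave therapy to patients with a diabetic foot wound, assessed by" recruitment, adherence, follow-up, exclusions and drop-outs. Wound healing is secondary: "Change in wound volume – assessed on 3D imaging". The Follow-up section has measurements at baseline and after the third treatment, and then "Wound imaging, quality of life and pain scores will then be repeated at weeks 4, 8 and 12".

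The Quantitative Data paragraph under Method of Analysis gives continuous outcomes as means and SDs and "categorical outcomes as counts and percentages as at all available follow-up points". It continues: "Any change in outcomes will be presented with 95% confidence intervals". It names no model, missing-data method or sensitivity analysis, and does not say whether change is paired within patient. Drop-out is to be described by counts and by reasons where known.

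Trial Exit says that participation ends completely on any of a list of events. These include withdrawal for health concerns or non-compliance, "Undergo angioplasty, bypass grafting or further surgery", any adverse event or reaction, and death.

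**The concern.** The phrase about available follow-up points may mean no more than every scheduled visit. The effect is the same: with no model or imputation, each visit's summary rests on those still attending. Several exit events (revascularisation, further surgery, withdrawal on health grounds) are plausible markers of a wound that is doing badly. If so, the group seen at week 12 is selected for doing well. The mean change then tilts toward benefit, and its 95% interval is centred on the wrong value. With one arm, no comparison group shares and offsets the selection. Assessing clinical outcomes is a stated aim and the report is meant for publication, so these figures will be read.

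The words quoted on available follow-up points belong grammatically to the categorical outcomes. The point rests mainly on the means and SDs in the same sentence and on the sentence about change.

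**Working it through.** **Nothing to reproduce.** The plan says "The sample size will be 40. This is appropriate for a feasibility study" and gives no effect size, SD, drop-out rate or target precision. The 40 is not shown to be wrong. For precision only, the 95% half-width is t(0.975, n−1)/√n. In SDs of change that is 0.32 at n=40, 0.34 at n=36 and 0.39 at n=28.

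**A rough guide to the exit rate.** The Introduction says 30–45% of diabetic digital amputations fail to heal, with 75% then having a higher amputation within the year. So 0.30×0.75 = 22.5% to 0.45×0.75 = 33.8% a year. With a constant hazard (an assumption), 1−(1−0.225)^(12/52) = 6% and 1−(1−0.338)^(12/52) = 9% over 12 weeks. Other exits would add to this. The protocol gives no rate.

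**Simulation 1: log wound volume.** n=40; visits at weeks 0, 1, 4, 8 and 12. Assumed: intercept SD 0.8, slope mean −0.08 and SD 0.10 per week, error SD 0.25. Exit is possible after week 4 or 8 if the recorded wound is no smaller than at baseline. True reduction: 1−exp(−0.08×12) = 62%.

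| Exits | Paired change in those present |
|---|---|
| 5–7% | 64–66% |
| 14% | 69% |
| 20% | 73% |
| 29% | 77% |

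At 14–29% exits the mixed model gave 61–62%. With slope SD 0.05, 9% exits gave 64%. For scale, the SD of change is √(1.2²+2×0.25²) = 1.25 log units. At n=37 the interval around the true value is −0.96 ± 0.42, a reduction of 42% to 75%.

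With no true healing and about 40% exits on recorded values, those present showed a false 38–41% reduction and the mixed model about zero. When exit instead followed the unseen current value (39% exits), those present showed a false 45% and the mixed model still a false 12–13%.

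**Simulation 2: bias at week 12 with true change zero.** n=40, 1,500 replicates, in units of the between-patient baseline SD; negative means false shrinkage. Ranges cover the assumed slope and residual SDs (0.8/0.3, 0.8/0.5, 0.5/0.5).

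| What drives exit | Exits | Difference in visit means | Paired change | Mixed model | Paired 95% interval misses truth |
|---|---|---|---|---|---|
| Nothing related to healing | 30% | about 0 | about 0 | about 0 | 4–6% |
| Last recorded change | 10% | −0.02 to −0.06 | −0.07 to −0.08 | about 0 | 7–8% |
| Last recorded change | 30% | −0.05 to −0.15 | −0.18 to −0.23 | about 0 | 20–24% |
| Unseen current value | 10% | −0.05 to −0.09 | −0.10 to −0.12 | −0.05 to −0.07 | 10–11% |
| Unseen current value | 30% | −0.13 to −0.25 | −0.26 to −0.34 | −0.15 to −0.21 | 41–49% |
| Underlying slope | 10% | −0.07 to −0.12 | −0.07 to −0.12 | −0.06 to −0.09 | 9–12% |
| Underlying slope | 30% | −0.20 to −0.32 | −0.20 to −0.32 | −0.17 to −0.26 | 24–56% |
| Healed patients leave | 30% | +0.05 to +0.15 | +0.19 to +0.22 | about 0 | 21–22% |

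At 30% exits the mixed model removes about 97% or more of the paired bias when exit follows recorded values. It removes 37–50% when exit follows the unseen value and 15–26% when it follows the slope. A random-slope model on 40,000 simulated patients agreed (95–105%, 41–52% and 16–29%). Pairing alone does not cure the problem. Against the simple difference in visit means the mixed model is not always better: with both SDs at 0.5 and 30% exits on the unseen value, the biases were −0.13 and −0.17.

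**The case against.** The strongest reply is that this is a small descriptive feasibility study with no hypothesis test. Follow-up rate and drop-out reasons are primary outcomes, and amputation is recorded at each contact, so readers will see who left and why. That stands, and it limits the severity. But listing reasons does not correct the means or the intervals printed beside them.

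A second reply is that the size rests on chosen inputs. It does. At exits near the 6–9% guide the distortion is small beside the sampling error, and even the 14% and 20% rows (69% and 73%) lie inside the 42–75% interval. Adverse-event exits may come early, since treatment falls within 7 days, and the reactions the protocol lists (itching, burning, pain, pigmentation) need not track healing.

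Three stronger readings are tempting and are not supported:

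- A reader might infer that exits will create apparent improvement. The documents give neither rate nor cause, and healed patients leaving would push the other way.
- A reader might infer that a mixed model would largely remove the bias. That holds only if exits depend on recorded values. Surgery can fall in the three- to four-week gaps between images, after deterioration nobody measured.
- A reader might infer that pain and quality of life are shown to be biased. Only wound volume on a log scale and a generic continuous outcome were simulated. Log volume is also undefined for a healed wound, and the plan uses arithmetic means.

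Finally, wound volume does not exist after death or amputation of the wounded part, and a mixed model implicitly extrapolates one. That stands too, and is why the model should not be the only addition.

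**Conclusion.** The concern holds as a risk. The plan combines exits that are complete and plausibly linked to poor healing with summaries of whoever remains, and states no missing-data method. If the link is real, the distortion is small at 5–10% exits and material at 20% or more. With true change zero, the paired bias is 0.07–0.12 baseline SDs at 10% exits and 0.18–0.34 at 30%. The nominal 95% interval then misses the truth in about 7–12% and 20–56% of trials.

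These sizes rest on assumed variances, exit rates and exit mechanisms. A mixed model is less biased than paired change in every poor-healing scenario examined, but it is close to unbiased only when exits follow recorded values. The outcomes are secondary, so this should be changed but does not undermine the feasibility aim.

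**What to change.** Amend Method of Analysis as follows:

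1. Keep the raw means and SDs. Beside them show the number observed and the reasons for missing data at each visit.
2. Report change at weeks 4, 8 and 12, with 95% intervals, from a likelihood-based mixed model for repeated measures. Use visit as a fixed effect, all observed visits including baseline, and within-patient correlation. Fix in advance a scale for wound volume that allows zero, and a simpler covariance structure in case the model does not converge (five visits unstructured need 5×6/2 = 15 parameters from 40 patients).
3. State that the model corrects exits that follow recorded values, and only partly corrects exits after unrecorded deterioration.
4. Tabulate outcomes for all enrolled participants, counting exit for amputation, further surgery, revascularisation or death as not improved. This also serves the categorical outcomes, to which a linear mixed model does not apply.
5. Add a sensitivity analysis, such as delta adjustment, for exits that depend on unseen values.

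The cost is analysis wording and a little programming in SPSS, which the plan already names; no new data are needed. The drawbacks are reliance on a missing-at-random assumption in step 2 and a possibly less favourable estimate of change.

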The PiezoWave 2 FBL 10x5 G2 device will be used to deliver extracorporeal shockwave therapy.

Safety and Tolerability

The device will only be used by trained staff members familiar will be device and deliverance of treatment. The environment of application of treatment will be equipped for emergency situations.

Ethics and Safety Reporting

Ethical approval will be sought from IRAS and the recruitment of participants will be in line with the declaration of Helsinki (2008). All patients will be informed of the study purpose, design, treatments, duration, risk and benefits and allowed to clarify additional questions during the consenting procedure. All participants must give informed consent and the consent form must be signed by the relevant parties, dated and kept with the

clinical trial forms in the patient's notes. The participant will be informed if any new information arises and informed consent must be gained again before carrying on with the trial.

The device will be used under the licensed indications and there are no anticipated adverse reactions. All adverse events or reactions and device failure will be reported on specific forms and action will be taken to treat the patient. If the event is deemed to be a serious adverse event or reaction the principal investigator will be informed within 24 hours. If an adverse event or reaction occurs the investigator will collect all possible information and the Principal Investigator will be informed to undertake the necessary action. Previous adverse reactions reported in the literature associated with extracorporeal shockwave therapy include: itching, burning, pain, skin pigmentation (12). Each participant will be given emergency contact details for the Principal Investigator if any concerns develop about the trial.

The trial will also comply with HEY research and development standards.

Withdrawals and Drop Outs

Patients are permitted to drop out at any point during the trial. The research investigators reserve the right to withdraw any participant if their health is at risk or if the participant fails to comply with the study protocol. If the subject develops an adverse event or reaction they will also be withdrawn from the trial.

Trial Exit

Participants will exit the trial completely when they complete the follow up period or if they:

- Withdrawn their consent to continue
- Withdrawn by the investigator due to health concerns or non-compliance

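### Discretionary withdrawal for non-compliance is a complete exit, so the follow-up rate can depend partly on investigator decisions about adherence, and week 4–12 data can be selected towards compliers

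*Combined protocol and SAP*

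**What the plan says.** Outcome measures lists five components of the primary feasibility outcome. Among them are "Adherence in treatment", the follow-up rate and the reasons for drop-out.

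Withdrawals and Drop Outs says: "The research investigators reserve the right to withdraw any participant if their health is at risk or if the participant fails to comply with the" protocol. Trial Exit begins "Participants will exit the trial completely when they complete the follow up period or if they" and includes in its list "Withdrawn by the investigator due to health concerns or non-compliance". The same list has exits unrelated to adherence: withdrawn consent, an adverse event or reaction, death, and "Undergo angioplasty, bypass grafting or further surgery".

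Study Treatments places all three sessions within 7 days. Under Assessments, wound imaging, quality of life and pain are repeated at weeks 4, 8 and 12.

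Method of Analysis says "Compliance with treatment will be presented descriptively", and that follow-up rates and known reasons for drop-out will be described. Outcomes are summarised at whichever follow-up times have data. No section defines non-compliance, says when the right to withdraw will be used, keeps a withdrawn participant under observation, or fixes a denominator for adherence or follow-up.

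**The concern.** Non-compliance is something this study exists to measure, and it is also an optional reason to stop measuring. Treatment is over within the first week, so a participant who misses a session could still be seen at weeks 4, 8 and 12. One investigator might withdraw that participant, and another might keep the same participant in follow-up. The follow-up rate would differ between the two although the participant's willingness to attend had not changed.

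Two things are at stake. First, a later trial that follows non-adherers would want to plan retention from this study's follow-up rate, and that rate may include an unstated amount of investigator choice. Second, wound volume, quality of life and pain at weeks 4 to 12 may under-represent people who found the treatment hard to complete. Those people are the most informative about acceptability, tolerability and logistics, which the Introduction gives as the gap the study is meant to fill.

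Health risk is a separate ground in the same sentence, so the non-compliance ground is not what protects participants' health.

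**Working it through.** **The plan's own figure.** Sample Size says "The sample size will be 40. This is appropriate for a feasibility study". No precision target, drop-out allowance or other basis for calculation is given, so the 40 cannot be reproduced. It is used below only as a denominator. The point rests on reading the rules together, and the arithmetic only shows what size the effect could be.

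**The rules side by side.**
1. Failing to comply with the protocol permits withdrawal by the investigator (Withdrawals and Drop Outs).
2. Withdrawal by the investigator for non-compliance is a complete exit (Trial Exit).
3. No section provides for assessments after exit.
4. Adherence and follow-up rate are both primary components (Outcome measures).

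Steps 1 to 3 give a route from non-adherence to lost follow-up that runs through an investigator's decision. Step 4 means that both ends of the route are primary outcomes.

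**Illustration.** Only the 40 comes from the protocol. The other inputs are assumptions:
- k = number of participants who miss at least one session
- w = share of those k whom investigators withdraw
- f = week-12 attendance among compliers
- g = week-12 attendance among non-compliers who are not withdrawn

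Follow-up rate = [(40 − k)·f + k·(1 − w)·g] / 40.

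The gap between withdrawing none (w = 0) and all (w = 1) is k·g / 40.

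| k | f | g | None withdrawn | All withdrawn | Gap |
|---|---|---|---|---|---|
| 10 | 0.9 | 0.9 | (27 + 9)/40 = 90% | 27/40 = 67.5% | 22.5 points |
| 10 | 0.9 | 0.5 | (27 + 5)/40 = 80% | 27/40 = 67.5% | 12.5 points |
| 4 | 0.9 | 0.9 | (32.4 + 3.6)/40 = 90% | 32.4/40 = 81% | 9 points |

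Withdrawing half of the 10 in the first row gives (27 + 4.5)/40 = 78.75%, so intermediate practice gives intermediate rates.

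**Selection of the follow-up data.** With k = 10 and f = g = 0.9, non-compliers supply 9 of 36 week-12 records (25%) if none is withdrawn. They supply 4.5 of 31.5 (14.3%) if half are, and none if all are.

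**Scale.** The normal-approximation 95% half-width for a proportion of 0.5 with n = 40 is 1.96 × √(0.25/40) = 0.155, or 15.5 points. The first gap in the table exceeds that and the other two do not.

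**The case against.** The strongest reply is that the rule is only a reserved right. Trial Exit applies once an investigator has actually withdrawn someone, and a non-complier who is not withdrawn remains in the week 4, 8 and 12 assessments. That stands. A reader might infer that adherence determines the follow-up rate, or that the later data come only from compliant participants. The second would require every non-complier to be withdrawn, and the first would also require that nobody be lost for any other reason. The protocol commits to neither, and it lists several other exits.

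Non-compliance also refers to the whole protocol and not just to treatment sessions. If the breach is itself missed visits, the lost follow-up is real and the rule did not create it. In the formula g is then close to zero and the gap disappears. This stands as a limit on the point.

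A reader might further infer that one missed session must be scored as an adherence failure, a drop-out and a loss to follow-up, or that withdrawn participants leave the denominator, so that adherence reads 30/30 = 100% instead of 30/40 = 75%. No section says either. Method of Analysis promises compliance and known drop-out reasons, and investigator withdrawals could be shown separately under that text, which would let a planner bound retention with and without them. But the plan does not require this, and showing the withdrawals does not recover the unobserved weeks.

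Finally, the protocol sets no follow-up threshold that a shifted rate would cross. That limits the consequence, although the rates are still the study's main product.

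**Conclusion.** The concern holds in a limited form. Undefined, discretionary withdrawal combined with complete exit can make the follow-up rate depend partly on investigator decisions about adherence, and can tilt the week 4, 8 and 12 data towards compliers. Reporting reasons for drop-out lessens the problem but does not remove it.

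The size cannot be known from the documents. With 10 non-compliers among 40, the all-or-none contrast is 22.5 points if they would attend as often as others (90%) and 12.5 points if they would attend at 50%. With 4 non-compliers at 90% it is 9 points. Each figure compares the two extremes of investigator practice and rests on assumed numbers of non-compliers and assumed attendance, so actual practice would probably give less. The change is worth making because it is cheap and protects a primary outcome. The documents do not support a claim that the follow-up rate will be unusable.

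**What to change.** Amend Withdrawals and Drop Outs and the Trial Exit list so that non-compliance alone does not end data collection. Then state that:

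- missed or incomplete sessions are recorded as non-adherence, and missed visits as missed visits, with reasons where known;
- these participants stay in the week 4, 8 and 12 assessments unless they withdraw consent or another listed exit applies;
- adherence and follow-up rate are reported over all consented participants, with any investigator withdrawals counted separately by reason.

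The amendment concerns data collection only. It leaves unchanged the health-risk ground, the other listed exits and any decision about stopping treatment.

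The cost is a short protocol amendment, a few more follow-up assessments in people who missed sessions, and possibly a less favourable adherence figure. The extra visits should be a small burden, since the protocol already intends follow-up to coincide with routine dressing and clinic appointments where possible.
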